4.1. Confidence intervals and p-values

Statistical tests and 97.5% confidence intervals for non-inferiority comparisons will be one sided-sided. Statistical tests and 95% confidence intervals for superiority and equivalence comparisons will be two-sided. P-values will be presented where appropriate.

For the primary endpoint (non-inferiority and subsequently superiority testing) no statistical multiplicity adjustment will be needed because of the closed testing principle (6,7). If in the primary endpoint the intervention fulfills the non-inferiority criterion, secondary endpoints which may become the basis for additional claims will be evaluated hierarchically (8). Statistically significant effects in these secondary endpoints, which are part of our confirmatory strategy, could be considered for additional claims. Clinically relevant secondary endpoints are listed separately and will be evaluated independently of the result of the primary endpoint. They would require further investigation if significant differences were observed, but the primary objective has not been achieved. For the secondary endpoints expressing supportive evidence, no claims are intended, and only descriptive statistics will be presented.

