- We added a sensitivity analysis for the primary endpoint using imputation for VLs missing at 24 months in the ITT population.
- We added a sensitivity analysis for the primary endpoint in a per-protocol population including participants for whom all viral loads were available in the VITALapp ≤31 days after phlebotomy.

Primary endpoint	Population	Comparison
Proportion of participants engaged in care	ITT	i. Non-inferiority
(defined as documented visit attendance) with documented viral suppression (< 50 copies/mL) 24 months (16-28 months) after enrollment*		ii. Superiority

Sensitivity analysis for the primary endpoint

1.	Proportion of participants engaged in care	ITT	13.:
	(defined as documented visit attendance)		i. Non-inferiority
	with documented viral suppression (<1000 copies/mL) 24 months (16-28 months) after enrollment		ii. Superiority

 Proportion of participants engaged in care (defined as documented visit attendance) with documented viral suppression (<50 copies/mL) 24 months (16-28 months) after enrollment ITT using imputation for VLs missing at 24 months

PP*

 Proportion of participants engaged in care (defined as documented visit attendance) with documented viral suppression (<50 copies/mL) 24 months (16-28 months) after enrollment

4.	Proportion of participants with viral re-	ITT	45. hierarchical (i.e. 4.
	suppression (< 50 copies/mL) 24 months (16-		only if the primary
	28 months) after enrollment among all		endpoint is non-inferior,
	participants with an unsuppressed VL (≥ 50		and 5. only if 4 is
	copies/mL) during the first 12 months of		superior):
	follow-up		Superiority
	•		, ,
5.	Proportion of participants with sustained	ITT	
	viral suppression (defined as >1 VL <50		
	copies/mL) during 24 months follow-up		
	ondary endpoints indicative of clinical		
ber 6.	nefit or harm Rate of mortality at 12 and 24 months after	ITT	67.: Equivalence
٠.	enrollment		8.: Superiority
			on superiority
7.	Proportion of participants with confirmed TB		
	diagnosis at 12 and 24 months after		
	enrollment		
8.	Disengagement from care at 12 and 24		
	months after enrollment		
	ondary endpoints expressing supportive		
	dence Time to follow-up VL in case of an	ITT	913.: Superiority (for 9
9.	unsuppressed VL (≥ 50 copies/mL)	111	11. the upper bound of
	unsuppressed vi (2 30 copies/inii)		the 95% CI must be below
10	Time to ART regimen adaption in case of		1, and for 1213. the
10.	virologic failure**		lower bound of the 95% C

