6.2. Analysis methods

General: Continuous variables will be inspected using histograms: 1) to assess for outliers which may be queried for accuracy, and 2) to assess whether appropriate transformations are required for the regression model. Outcomes will be summarized using medians and interquartile ranges for

continuous variables and numbers and percentages for categorical variables, by randomized group. Percentages will be reported to one decimal place. For the primary outcome and its sensitivity analyses, we will report adjusted odds ratios and adjusted risk differences derived from regression models. If a model fails to converge using the identity link function (for estimating the adjusted risk difference), only adjusted odds ratios will be reported. Methods for secondary analyses are detailed below; for secondary analyses aligned with the primary outcome analysis, we will report adjusted odds ratios. If the number of outcome events is insufficient to support reliable coefficient estimation (e.g., fewer than 10 events per parameter), no regression model will be fitted. We will consider the day of enrolment until the day of primary endpoint VL or until 28 months after enrolment if endpoint VL missing as study period for each participant.

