Effect modification (primary outcome): For effect modification of the primary outcome the following variables will be considered:

- i. Age groups (18-24, 25-39, 40-59, and ≥60 years)
- ii. Gender (female, male)
- iii. Cell phone access (yes, no)

Analyses will be performed as for the main primary outcome analysis including an interaction term between these potential effect modifiers and the randomized group. If an interaction term is found to be significant (p-value<0.05), effect estimates will be summarized descriptively by subgroup categories. As the study is not powered for these pre-planned subgroup analyses, no formal hypothesis testing will be done.

Secondary endpoints which may become the basis for additional claims: In case non-inferiority of the primary endpoint is established, these will be evaluated hierarchically.

- 4. Proportion of participants with viral re-suppression (<50 copies/mL) 24 months (16-28 months) after enrollment among all participants with an unsuppressed VL (≥ 50 copies/mL) during the first 12 months of follow-up: This analysis will include individuals with a VL ≥50 copies/mL in the first 12 study months and then directly follow the primary endpoint analysis.
- 5. Proportion of participants with sustained viral suppression (defined as >1 VL <50 copies/mL) during 24 months follow-up: This analysis will directly follow the primary endpoint analysis with endpoint adapted to sustained viral suppression <50 copies/mL throughout the study. Sustained viral suppression is defined as >1 VL <50 copies/mL from study start to end of 24-month window (0-28 months) along with no VL ≥50 copies/mL.

Secondary endpoints indicative of clinical benefit or harm: These will be evaluated independently of the primary objective and without hierarchy / multiplicity adjustment.

- 6. **Rate of mortality at 12 and 24 months after enrollment:** This analysis will use Cox regression adjusted for clinic and district by study arm.
- 7. **Proportion of participants with confirmed TB diagnosis at 12 and 24 months after enrollment:** This analysis will directly follow the primary endpoint analysis with endpoint TB diagnosis (window: 0 months to primary endpoint or 28 months).
- 8. **Disengagement from care at 12 and 24 months after enrollment:** This analysis will directly follow the primary endpoint analysis with endpoint disengagement from care at 24 months, defined as neither a documented visit attendance nor a VL measurement (window: 16-28 months).

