Secondary endpoints expressing supportive evidence:

- 9. Time to follow-up VL in case of an unsuppressed VL (≥ 50 copies/mL): This analysis will consider the time in weeks to follow-up VL in case of an unsuppressed VL (≥ 50 copies/mL) as outcome and use a multi-level linear regression model including clinic cluster as a random effect, arm allocation and the randomization stratification factor (district) as a fixed effect.
- 10. Time to ART regimen adaption in case of virologic failure: This analysis will consider the time in weeks to ART regimen adaption in case of virologic failure (defined as two consecutive VLs ≥1'000 copies/mL or three consecutive VLs ≥20 copies/mL from VITAL start 22.12.2022 and two consecutive VLs ≥50 copies/mL from 23.12.2022 − VITAL closure) as outcome and use a multi-level linear regression model including clinic cluster as a random effect, arm allocation and the randomization stratification factor (district) as a fixed effect.
- 11. Rate of clinic visits at 24 months after enrollment: This analysis will consider the number of clinic visits throughout the study period as outcome and use and use a multi-level Poisson regression model with offset study duration including clinic cluster as a random effect, arm allocation and the randomization stratification factor (district) as a fixed effect.
- 12. Proportion of participants with ART regimen modification due to virologic failure at 12 and 24 months among participants with virologic failure: This analysis will only include people with a virologic failure (defined as two consecutive VLs ≥1′000 copies/mL or three consecutive VLs ≥20 copies/mL from VITAL start 22.12.2022 and two consecutive VLs ≥50 copies/mL from 23.12.2022 VITAL closure). Then, this analysis will directly follow the primary endpoint analysis with endpoint ART modification.
- 13. **Proportion of participants having ever received TPT:** This analysis will directly follow the primary endpoint analysis with endpoint having ever received TPT by 24 months.

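### Table 3 tests endpoints 9 and 10 against 1, but section 6.2 models them as weeks in a linear regression (null 0) and gives no rule for people without the event

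*SAP*

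**What the plan says.** Section 6.2, endpoint 9: "This analysis will consider the time in weeks to follow-up VL in case of an unsuppressed VL", "as outcome and use a multi-level linear regression model including clinic cluster as a random effect", with arm and district as fixed effects. Endpoint 10, time in weeks to regimen adaption after virologic failure, has the same model. Endpoint 11, the clinic visit rate, has a multi-level Poisson model.

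Section 6.1, Table 3, lists 9 to 13 as superiority comparisons. One criterion covers 9 to 11: the upper bound of "the 95% CI must be below" 1.

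Section 6.2 (General) provides for inspecting continuous variables "to assess whether appropriate transformations are required for the regression model", without naming a transformation or tying it to endpoint 9 or 10. It defines each person's study period as "the day of enrolment until the day of primary endpoint VL or until 28 months after enrolment if endpoint VL missing as study period", with no censoring rule attached. In section 6.3 the failure rule and the imputation concern the primary outcome only.

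Section 4.1 says of the supportive endpoints that "no claims are intended, and only descriptive statistics will be presented".

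**The concern.** There are three faults.

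1. **Wrong null.** A linear model of weeks gives a mean difference, for which no effect is 0. A limit of 1 therefore only excludes a delay of one week or more. An estimate of +0.3 week with standard error 0.3 has a 95% interval of 0.3 ± 1.96 × 0.3, or -0.29 to 0.89. It would count as superior although the intervention arm was slower.

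2. **No rule for people without the event.** Someone never retested, or never given a regimen change, has no value for a linear model of time. If such people drop out by default, the comparison is restricted to those who had the event, which the intervention may itself influence.

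3. **Status of these endpoints.** Descriptive statistics only (4.1), superiority criteria (Table 3) and regression models (6.2) cannot all be followed.

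Endpoints 9 and 10 describe how quickly a model of care triggered by viral load acts on a result, so the reported figures should be interpretable and should not depend on which analyst ran them.

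**Working it through.** The plan gives no figure for these endpoints to reproduce, so the check compares the passages and then sizes the consequence under stated assumptions.

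**Scale and null**

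| Endpoint | Model in 6.2 | Arm effect | Null | Table 3 limit |
|---|---|---|---|---|
| 9 | linear, weeks | difference | 0 | 1 |
| 10 | linear, weeks | difference | 0 | 1 |
| 11 | Poisson | rate ratio | 1 | 1 |

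The general sentence on transformations does not settle this. A limit of 1 is right only for an exponentiated coefficient of log time. On the unexponentiated log scale, a limit of 1 means a time exp(1) = 2.72 times as long.

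**Chance of being called superior.** For a true difference d in weeks and standard error SE, P(upper limit < 1) = Φ((1 − d)/SE − 1.96). With the limit at 0 it is Φ(−d/SE − 1.96).

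| SE (assumed) | d = 0, limit 1 | d = 0, limit 0 | d = 0.5, limit 1 | d = 0.5, limit 0 |
|---|---|---|---|---|
| 1 week | 16.9% | 2.5% | 7.2% | 0.7% |
| 2 weeks | 7.2% | 2.5% | 4.4% | 1.4% |
| 4 weeks | 4.4% | 2.5% | 3.3% | 1.9% |

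**Range of SE.** The inputs are 9 clinics per arm and the intraclass correlation of 0.04 (both section 3.3, the latter set for the primary endpoint), plus an assumed SD and an assumed number m of contributing people per clinic. SE = √(2 × SD² × (1 + (m − 1) × 0.04)/(9m)).

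- SD 7.3, m = 40: √(2 × 53.29 × 2.56/360) = 0.87; pass rate at no effect 21%.
- SD 10, m = 20: √(2 × 100 × 1.76/180) = 1.40; 11%.
- SD 20, m = 10: √(2 × 400 × 1.36/90) = 3.48; 5%.

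**People without the event.** The plan expects them: endpoint 12 is "Proportion of participants with ART regimen modification due to virologic failure at 12 and 24 months among participants with virologic failure", in the same group as endpoint 10. For endpoint 9, if follow-up stops with the study period, a first unsuppressed result that is itself the endpoint viral load can have no follow-up result.

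The illustration assumes T = 26 weeks of follow-up and exponential times with mean μ in a fraction p who would ever have the event. With F = 1 − exp(−T/μ), the share observed is pF, the mean among those observed is μ − T·exp(−T/μ)/F, and the restricted mean is pμF + (1 − p)T.

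| Case | Arm | p | μ (weeks) | Observed | Mean if observed | Restricted mean |
|---|---|---|---|---|---|---|
| a | control | 1 | 37.5 (median 26) | 50.0% | 11.5 | 18.8 |
| a | intervention | 1 | 23.1 (median 16) | 67.6% | 10.6 | 15.6 |
| b | control | 0.9 | 14 | 75.9% | 9.2 | 13.2 |
| b | intervention | 0.6 | 10 | 55.5% | 7.9 | 16.0 |

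In case a, a true gain of 3.2 weeks (18.76 − 15.60) shows as 0.9 (11.51 − 10.61). In case b, the intervention looks 1.3 weeks faster (9.19 − 7.91), although its restricted mean is 2.7 weeks longer (15.95 − 13.23).

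**The case against.** The strongest reply is that little depends on this. The endpoints are supportive, outside the hierarchy, and no claims are intended. The criterion in Table 3 is probably a drafting slip that grouped three endpoints where lower is better. Section 4.1 foresees two-sided superiority tests, and software tests a linear coefficient against 0 by default. That limits the practical harm, but it does not make the written criterion correct.

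The sizes are also assumptions. The SAP gives no SD, SE or count for these endpoints. The 21% combines the smallest assumed SD with the largest assumed clinic size, and nothing in the SAP suggests the pattern in case b. This stands: the calculations show direction and possibility, not expected size. The direction of the threshold error holds at any SE.

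Endpoint 12 would make a difference between arms in regimen changes largely visible, which partly offsets the gap for endpoint 10. Endpoint 9 has no such companion. Section 6.2 also withholds a regression when events are too few (for example, under 10 per parameter), so the model for endpoint 10 may never be fitted.

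Finally, changing the model during analysis introduces a post-hoc choice, and the Cox model of endpoint 6 ("This analysis will use Cox regression adjusted for clinic and district by study arm") specifies no clinic random effect, so it is only a partial precedent. Both are reasons to log and disclose the change and to keep a minimum fix available. They are not reasons to leave the text as it is.

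**Conclusion.** The concern holds. The limit of 1 is wrong for endpoints 9 and 10 as modelled and right for endpoint 11. Under no effect, the literal criterion passes more often than 2.5% at any SE: 21% down to 5% over the assumed SE range of 0.9 to 3.5 weeks. No section covers people without the event, and leaving them out can bias the comparison in either direction; how far depends on inputs the SAP does not give. Section 4.1 conflicts with both Table 3 and 6.2 for endpoints 9 to 13. The correction should be made, but its reach is confined to supportive endpoints; the primary conclusion does not change.

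**What to change.** - **Threshold.** Keep the limit of 1 in Table 3 for endpoint 11 only. For 9 and 10, name one effect measure and its null. The minimum is an upper limit below 0 weeks for a mean difference, or below 1 if a ratio of times from a log-time model is stated in advance.
- **Model (preferred).** Use a censored time-to-event model, for example Cox with a clinic random effect and fixed effects for arm and district, censored at the end of the section 6.2 study period. Shorter time then means a hazard ratio above 1, so the criterion becomes a lower 95% limit above 1. Someone whose first unsuppressed result falls on the last study day contributes no time at risk; the text should say so.
- **People without the event.** Under either model, state how they, deaths and transfers out are treated, and report the number without the event by arm. Censoring at death or transfer may be informative, so consider a competing-risks analysis.
- **Status.** Drop either the superiority criteria for 9 to 13 or the descriptive-only wording in 4.1, and align 6.2 with the choice.

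The threshold costs one line of wording. The time-to-event model needs no new data, but it is a change made during analysis. It should be logged in section 1.4 and disclosed, ideally with the linear result shown alongside.

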3.7. Timing of outcomes assessment

Table 2 shows the nominal visit months, the permitted ranges according to the protocol, and the ranges that will be used for analysis.

Nominal visit month	Window according to the protocol in months	Range used for analysis
12	4-16 months	- Months will be analysed as calendar months, i.e., for a participant enrolled on 10.10.2020 the 24 months window will be 10.02.2022 -10.02.2023.
24	16-28 months	If multiple viral loads are available in the outcome window, the closest measurement to the nominal visit month will be considered for analysis.

Table 2. Nominal visits and permitted windows.

4. Statistical principles

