5.5. Baseline participant characteristics

Baseline participant characteristics will be summarized by group, using medians and interquartile ranges for continuous variables and numbers and percentages for categorical variables. There will be no formal testing for baseline characteristics differences across randomized groups (9,10).

6. Analysis

Analyses will follow CONSORT guidelines, including extensions for non-inferiority trials (11,12). Analyses will include all follow-up to the date of data freeze; as well as documented and reasoned changes thereafter.

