	virologic failure		must be above 1)
11.	Rate of clinic visits at 24 months after		must be above 1,
	enrollment		
12.	Proportion of participants with ART regimen		
	modification due to virologic failure at 12		
	and 24 months among participants with		
	virologic failure**		
12	Proportion of participants having ever		
	opo. don or participants naving ever		

Table 3. Primary and secondary endpoints as well as sensitivity analyses. *The per-protocol analysis includes participants for whom all viral loads were available in the VITALapp ≤31 days after phlebotomy. **Virologic failure is defined according to the implementation in VITAL, i.e. two consecutive VLs ≥1'000 copies/mL or three consecutive VLs ≥20 copies/mL from VITAL start - 22.12.2022 and two consecutive VLs ≥50 copies/mL from 23.12.2022 – VITAL closure.

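### Endpoint 12 scores late virologic failures as not modified without allowing time for a change, so its arm contrast can be biased by retest speed

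*SAP*

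**What the plan says.** Section 6.2 names the endpoint as "Proportion of participants with ART regimen modification due to virologic failure at 12 and 24 months among participants with virologic failure". On the denominator it says "This analysis will only include people with a virologic failure". On the analysis it says "Then, this analysis will directly follow the primary endpoint analysis with endpoint ART modification". That means the mixed logistic model, with clinic as a random effect and arm and district as fixed effects. No window, minimum follow-up, offset or censoring rule is given.

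Three other rules decide how much time a failure has:

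- **Study period** (section 6.2, general paragraph). Each participant's period runs from "the day of enrolment until the day of primary endpoint VL or until 28 months after enrolment if endpoint VL missing".
- **Endpoint viral load** (section 3.7). "If multiple viral loads are available in the outcome window, the closest measurement to the nominal visit month will be considered for analysis". The nominal month is 24 and the window is months 16 to 28.
- **Failure** (section 6.1, footnote to Table 3). It takes consecutive results, for example "two consecutive VLs ≥50 copies/mL from 23.12.2022", so it is dated by the confirming result.

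Table 3 gives endpoint 12 a superiority criterion: the lower 95% confidence limit must lie above 1. Section 4.1 says supportive endpoints carry no claims and are described only.

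**The concern.** One viral load can both confirm failure and close the participant's observation. That person stays in the denominator, has no time left for a regimen change, and is scored as not modified. Someone confirmed a few weeks earlier has only a few weeks. A logistic model of a yes/no outcome cannot separate no response from no time to respond.

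How often this happens depends on how soon an unsuppressed result is repeated. That interval is endpoint 9, which Table 3 lists for superiority, so the SAP itself allows for a difference by arm. Part of any contrast on endpoint 12 may then reflect testing speed while being read as a better or worse response to failure.

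The SAP deals with time elsewhere: endpoint 7 states its window, and endpoint 11 has an offset for study duration. Endpoint 10 does not fill the gap, because it is a linear model of time to adaptation with no stated rule for people never modified.

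**Working it through.** The SAP gives no expected proportion, failure count, retest interval or modification rate for endpoint 12, so there is no figure of its own to reproduce. The check applies its rules to assumed rates.

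**Time available.** Let C be the confirming viral load and S the end of the study period (the viral load closest to month 24 within months 16–28, or month 28 if there is none). Time for a modification is S − C.

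- Unsuppressed result at month 18, repeats every 3 months: results at 18, 21, 24; C = 21, S = 24, so 3 months remain. Repeats every 6 months: results at 18, 24; C = S = 24, so 0 days remain.
- Unsuppressed result at month 22, repeat after 3 months: C = 25 and S = 25 (1 month from 24, against 2), so the person is in the denominator with 0 days. Repeat after 6 months: the repeat falls at 28 (4 months from 24, against 2), S = 22, and the failure is confirmed after the period and leaves the denominator.

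The first case favours the faster arm. The second favours the slower one.

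**Response model (assumed, identical in both arms).** 80% are eventually modified, with an exponential delay of median 3 months: P(modified by t) = 0.8 × (1 − 0.5^(t/3)). This gives 0 at t = 0, 0.40 at 3 months and 0.60 at 6 months. In the month-18 case the arms would show 40% and 0% with the same response.

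**Simulated proportions modified by S,** with failure at the second consecutive unsuppressed result and OR = [p₁/(1−p₁)]/[p₂/(1−p₂)]:

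| Assumed pattern | 3-month retest | 6-month retest | OR |
|---|---|---|---|
| Uniform onset, routine viral load 6-monthly | 61.1% | 53.1% | 1.39 |
| Uniform onset, routine viral load 12-monthly | 57.1% | 48.6% | 1.41 |
| First unsuppressed result in months 0–12 | 76.5% | 72.0% | 1.27 |
| Late onset, routine viral load 12-monthly | 22.9% | 7.0% | 3.95 |
| Half in months 0–4, half in months 20–22 | 40.8% | 52.0% | 0.64 |

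With uniform onset, zero-day failures were 12–15% of the denominator at a 3-month retest and 25–28% at 6 months. In the last row the slower arm confirmed only 75.4% of cases within its study period, against 99.6%; its late failures had left the denominator.

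A second model (annual viral loads at random phase, modification hazard 0.1–0.4 per month) gave ORs of 1.48–1.89 for 3 versus 6 months and 1.19–1.41 for 3 versus 4.5 months.

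**Chance of meeting the Table 3 criterion with no difference in response.** With 100 failures per arm and clustering ignored, it is 21% at OR 1.39 and 22% at OR 1.41, against a nominal 2.5% in that direction.

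**If changes to month 28 count for everyone.** With uniform onset the results are 67.5% versus 66.4% (OR 1.05) and 65.0% versus 63.2% (OR 1.08), for 6- and 12-monthly routine tests. Time is still unequal, but the effect is small.

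**Clock started at confirmation.** At a 6-month horizon the true value is 0.8 × (1 − 0.5²) = 60%. With full follow-up the arms gave 61.0% versus 61.0% and 60.3% versus 59.2% with uniform onset, and 60.1% in both arms in the pattern that reversed the sign. Censoring at S in place of full follow-up also returned about 60% in both arms. A separate uniform-onset run, with naive ORs of 1.5–1.9, gave 70.5% versus 69.7% once censored this way.

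**The case against.** **Zero days needs the general study period to apply.** Endpoint 12 does not invoke it, whereas endpoints 7 and 11 do. This stands as a condition. But it is the only general end date given, and the month-28 reading leaves time unequal, though with little effect.

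**The direction and size are not established.** This stands. A reader might infer that the faster-retesting arm will look superior. The documents do not support that: the sign depends on when failures arise, and every rate above is assumed. The runs also use the two-result rule, which the SAP applies only from 23.12.2022. Before that, failure needed two results of at least 1,000 copies/mL or three of at least 20.

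**Nothing confirmatory is at stake.** Largely right. Section 4.1 rules out claims, and section 6.2 fits no model below about 10 events per parameter. Raw percentages by arm carry the same bias, however, and Table 3 still sets a superiority criterion.

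**Faster testing is part of the care model.** In a pragmatic trial, the share of failures modified by a study time point could legitimately include it. That is a coherent estimand, but this endpoint does not estimate it well, because its denominator also moves with retest speed.

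**Two further readings fail.** Section 6 opens with "Analyses will include all follow-up to the date of data freeze", which might seem to contradict the study period. One can be read as the data cut and the other as each participant's period within it, so the need is to say which governs. Nor does the endpoint allow changes made before failure: its definition says the modification is due to failure.

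**Conclusion.** The point holds as a weakness in a supportive analysis that should be corrected. Endpoint 12 gives failures unequal time that depends on retesting, and none at all when the endpoint viral load is the confirming result and the general study period applies. The arm contrast can then be biased with identical response to failure. For 3 versus 6 months and uniform onset, the main model gives ORs of about 1.4 and the alternative models 1.5–1.9. The range runs from 0.64 to 3.95 across the onset patterns tried, and from 1.05 to 1.08 if changes to month 28 count. If the arms retest equally fast, this route to bias closes. All these sizes rest on assumed retest gaps, onset patterns and modification rates.

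**What to change.** Define endpoint 12 from the date of the confirming viral load. Report the cumulative incidence of regimen modification at one fixed analysis horizon, for example 26 weeks, by arm, accounting for clinic clustering and district. The horizon is an analysis window, not a rule for care. Censor participants at the end of their study period, or at last available follow-up if treatment changes are recorded later, instead of scoring them as not modified. State which end date governs endpoint 12, report follow-up after confirmation by arm, and bring Table 3's superiority criterion into line with section 4.1.

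The cost is SAP wording and one re-derived variable; censoring at the existing end date needs no new data. Late failures will contribute little or no information. SAP V1.1 is dated during analysis, so the change must be reported as made at that stage, preferably with the existing proportion alongside.
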